where BAT and tDCS are dummy variables for interventions, AA is the dummy variable for African Americans. Linear contrast will be employed to test the main effect of BAT (corresponds to the test of $\beta_3 + \beta_6/2 + \beta_7/2 + \beta_9/4=0$) and tDCS (test of $\beta_4 + \beta_6/2 + \beta_8/2 + \beta_9/4=0$). These six tests (2 main effects for three primary outcomes) will be performed at one-sided $\alpha=0.0083$ significance level. In addition, point estimates and 95% confidence intervals will be obtained for the BAT and tDCS effects with or without the presence of the other treatment in the whole population or within AA and NHW subgroups. We will use normal probability plots to assess distributional assumptions of the models. The above analysis plan will be followed for other outcomes including resting state cerebral blood flow, disability and functional performance, as well as the analysis of changes of the outcomes from post-treatment to three-month follow-up.

For **Aim 2**, we will assess interactions between race and intervention. Point estimates and 95% confidence intervals will be obtained for the race difference in the effects of BAT and tDCS on each outcome. Because we expect the interaction effect to be smaller than the main effect, for formal hypothesis testing, we plan to pool evidence across three primary outcomes to test the ethnic group differences. Specifically, we will obtain a p-value corresponding to test the hypothesis $\beta_7=\beta_8=\beta_9=0$ for

each outcome based on the general linear model specified in the analysis plan for Aim 1. And Fisher's combination of three p-values will be used as the overall test statistic, which will be compared to the null distribution obtained through permutation of ethnic group variable.

For Aim 3, path models with strictly ordered relationships will be used to study the interventions' direct effects on clinical pain and disability and the indirect effect on the mediating variables including pain modulatory balance; resting state and stimulus-evoked pain-related brain function; perceived stress, pain catastrophizing, and mindfulness. We will construct additional analyses using pre-treatment variables as predictors of intervention effects. We will examine separate multivariable models for each ethnic group to determine whether mediators of treatment effects differ for AAs vs. NHWs.

Missing Data and Sensitivity Analysis: The four randomized groups will be compared in missing patterns in the primary outcomes including reasons for missing data, timing of missing data, and distributions of baseline covariates and earlier outcomes.

We will consider the following approaches to impute each of the primary outcomes: (1) the last-observation-carried-forward method; (2) missing primary outcome predicted by a fitted regression model using demographic and baseline clinical variables; (3) missing primary outcome predicted by baseline and available follow-up outcomes on a fitted regression model. The imputation method for the primary intent-to-treat analysis will be selected using cross-validation performed on the participants with complete data. Specifically, we will evaluate imputation accuracy based on 2,000 repetitions that randomly leave out 20% of the complete samples. In addition, to consider the uncertainty due to missing values, we will apply the SAS multiple imputation procedure to generate multiple imputed data sets using the selected imputation approach, and combine results from analyses of these data sets, e.g., to provide mean and variance of the treatment effect estimates. No imputation is planned for secondary outcomes. Missing data in secondary outcomes will be considered missing. For a subject to achieve a given secondary endpoint, that endpoint must be observed.

7. Possible Discomforts and Risks:

Potential risks are minimal and relate primarily to short-term discomfort of the sensory testing procedures delivering cold and mechanical pressure. The risks from brain imaging procedures are thought to be minimal in appropriately screened participants. Questionnaires include specific questions about how a participant feels and ask the participant to think about life experiences. Reading or answering these questions may cause some participants embarrassment or discomfort.

Potential Risks

Mechanical pressure: pressure is delivered by a hand-held algometer (spring-controlled device delivering calibrated pressure via a flat 10mm diameter rubber tip). Pressure is delivered at an approximate rate of 30 kPa/sec. Participants will be instructed to signal by pressing a button when the pressure sensation first becomes painful at which time the researcher removes the algometer. There is little opportunity for bruising or other transient trauma from this procedure. Also, mechanical punctate stimuli will be delivered using a nylon monofilament. Risk associated with this procedure is minimal.

Cold Stimulation: Cold is delivered by having subjects immerse their hand in cold water. This can produce temporary discomfort, which subsides with withdrawal of the hand. No other risks are known. Participants may stop at any time.

Magnetic resonance imaging (MRI): MRI is a procedure that allows doctors to look inside the body by using a scanner that sends out a strong magnetic field and radio waves. This procedure is used routinely for medical care and is very safe for most people, but participants will be monitored during the entire MRI scan in case any problems occur. The risks of MRI are:

- The MRI scanner contains a very strong magnet. Therefore, participants may not be able to have the MRI if they have any type of metal implanted in their body, for example, any pacing device (such as a heart pacer), any metal in their eyes, or certain types of heart valves or brain aneurysm clips. A MRI technologist will question participants about any contraindications before they enter the scanner.
- There is not much room inside the MRI scanner. Participants may be uncomfortable if they do not like to be in close spaces ("claustrophobia"). During the procedure, participants will be able to talk with the MRI staff through a speaker system, and, in the event of an emergency, participants can tell them to stop the scan.
- The MRI scanner produces a loud hammering noise, which has produced hearing loss in a very small number of participants. Participants will be given earplugs to reduce this risk, and headphones for added protection.
- If an obvious abnormality is discovered during the participant's MRI scan, they will be informed about it by the research team, and will be provided with a copy of the MRI scan and we will encourage them to see their primary care physician. MRI will only be done for research purposes in this study.
- Participants will be monitored very carefully while in the scanner, and repeatedly checked to ensure comfort.

Transcranial direct current stimulation: Transcranial direct current stimulation is considered safe but a small number of people do experience some side effects. The most common side effects are itching and tingling or mild discomfort at the area of stimulation, and headache. Other possible side effects include dizziness and nausea. Whenever an electrical stimulation is applied to the body, it could possibly cause a seizure or abnormal heartbeat, but this has never occurred with the transcranial direct current stimulation parameters used in this study.

Breathing and Attention Training (BAT): The brief BAT intervention in this study carries minimal risks. Some participants may become uncomfortable while focusing on their breathing and letting go of thoughts and feelings. We will instruct participants to alert the experimenter if they experience discomfort during the treatment.

Survey questionnaires: Potential risk involves participant feelings of discomfort or unease when reading or responding to survey questions that are personal. Throughout each questionnaire, participants are reminded that participation is completely voluntary, they can refuse to answer any question or can stop at any time.

Adequacy of Protection against Risks.

Our inclusion and exclusion criteria are designed to minimize risks to participants.

A total of 360 (180 African American, 180 non-Hispanic whites) adults with symptomatic knee osteoarthritis (OA), between 45 and 95 years of age will be enrolled. Half of these participants will be enrolled at UF and the other half at UAB. Similar to our previous work, the inclusion criteria for participants are:

- 1) Unilateral or bilateral symptomatic knee OA based on American College of Rheumatology Clinical criteria (1).
- 2) Age 45 – 95; this age range was chosen because the prevalence of knee OA is substantially lower before age 45, and participants over 95 years are increasingly likely to meet one or more exclusion criteria. This relatively broad age range will allow us to examine potential age-related influences on responses to the proposed interventions.
- 3) Participant reports primary ethnic/race group as either African American or non-Hispanic white.

Participants will be excluded if they have any concurrent medical conditions that could confound interpretation of outcome measures, pose a safety risk for any of the assessment or intervention procedures, or preclude successful completion of the protocol. Specific exclusion criteria are:

- Actively symptomatic systemic rheumatic disease/condition (e.g. rheumatoid arthritis, systemic lupus erythematosus), or fibromyalgia that results in pain outside the knee that is equal to or worse than the participant's knee pain.
- A history of clinically significant surgery to the index knee.
- Daily use of opioids. We will exclude patients using opioids daily as both continued use and temporary withdrawal from these medications this could affect pain perception and response to interventions. Other medications being used will be recorded and controlled in statistical analyses as needed.
- Use of some centrally acting sodium channel blockers and NMDA receptor antagonists, because some of these medications can block tDCS effects. Other medications can potentially influence response to tDCS (e.g. SSRIs, beta-blockers); therefore, consistent with recent recommendations (2), we will assess use of these medications and include them as covariates in our statistical models.
- Uncontrolled hypertension (i.e. SBP/DBP of $\geq 150/95$) or unstable or activity limiting cardiovascular or peripheral arterial disease. These exclusions are in place primarily for safety reasons, because the cold pressor task represents a cardiovascular challenge. However, uncontrolled hypertension can also affect pain perception, which is another reason for excluding these individuals.
- Neurological disease (e.g. Parkinson's, multiple sclerosis, epilepsy) or evidence of previous brain injury, including stroke and traumatic brain injury.
- Serious psychiatric disorder requiring hospitalization within the past 12 months or characterized by active suicidal ideation.
- Current substance use disorder or history of hospitalization for treatment of substance use disorder.
- Diminished cognitive function that would interfere with understanding of study procedures.
- Chronic pain is more severe at any other body site other than the knee

Protection against Risk.

Protection against risk to confidentiality. Information collected as part of this research protocol will be maintained in locked filing cabinets and password protected databases accessible only to study personnel. All study staff will be trained in handling human subject information to maintain privacy and confidentiality. Procedures for allowing access to investigators to use this information for research will be under the authority of the PI and will follow HIPAA compliant guidelines for the release of PHI.

No results will ever be reported in a personally identifiable manner. All research data will be entered directly into a web-based survey that is maintained by the University of Florida CTSI (REDCap). The data will be stored on secure servers at the University of Florida and will be accessible only to trained study personnel. A Certificate of Confidentiality will be obtained from the NIH for this project.

Protections of risks related to study questionnaires. To minimize any risks related to emotional responses to questionnaires, persons will be informed about the types of questions included in the surveys, which are similar to the types of questions persons might be asked by their doctor in a clinical setting. They will be informed that they can refuse to answer any questions if they so choose.

Protection of risks related to tDCS. To minimize risk associated with tDCS, participants will be monitored throughout stimulation sessions and asked to report any discomfort. If scalp sensation is uncomfortable, stimulation will be stopped. In the event of a headache, stimulation will be stopped. All tDCS sessions will be administered and continually supervise by a trained experimenter. The above symptoms have only been reported when participants are actively being stimulated. tDCS has

not been shown to cause seizures nor lower the seizure threshold in animals. There are no reports of seizure induced by tDCS in human participants in the literature. However, this may not be true for epilepsy patients, whose seizure threshold rates are likely abnormal. Prior history of neurological disorders is an exclusionary criterion for our study and thus no participants will have a history of seizure.

Protection against risks related to BAT. The BAT intervention carries minimal risk, however some individuals may become uncomfortable attending to their breathing and their thoughts and feelings. Participants will be encouraged to alert the experimenter if they experience discomfort, and the intervention will be halted.

Protection against risks associated with neuroimaging. MRI is widely regarded as a safe, noninvasive procedure for visualization of brain tissue in both adults and children. Prior to study participation, all participants will be informed of the MRI procedure during the informed consent/assent process. The proposed study will be performed on an FDA approved Siemens 3 Tesla scanner located at the Advanced Magnetic Resonance Imaging and Spectroscopy (AMRIS) research facility at UF. There are no known long-term effects of MRI procedures on the body. The FDA Information Sheets, Food and Drug Administration, October 1995, p. 79, lists as a non-significant risk device, "Magnetic Resonance Imaging (MRI) Devices within FDA-specified parameters." This study satisfies those parameters. The 3.0 tesla MR scanners meets FDA parameters for field strength, gradient switching, and RF power deposition for all FDA-approved acquisition schemes including echo-planar imaging. Both our study staff and trained MRI staff will check for exclusion criteria. The main MRI-related risks include: (a) sensitivity to the loudness of the MRI machine - all subjects will be given and must wear ear plugs; a squeeze-ball and microphone will be provided so that they may stop the testing if they become uncomfortable or anxious at any time; (b) claustrophobia - subjects will have the opportunity to practice in a simulator and to become as familiar and comfortable as possible before commencing the experiment. In addition, they will be given the opportunity to examine the scanner before the tasks starts. The study will be ended early if the space is a problem for them; no medications (e.g., benzodiazepines or tranquilizers) will be offered to them; (c) lightheadedness when sitting up after lying in the MRI machine - this feeling sometimes occurs but has always gone away in a few minutes. Participants will thus be assisted in getting up to make sure they do not fall; In sum, the MRI neuroimaging procedures pose no radiological or medical risk, given that participants with metal implants susceptible to magnetic heating will be excluded based on standard scanner policies. A small number of people may become anxious in the small space of the scanner. These individuals will have the opportunity to terminate the scan session. Furthermore, all recruits will be screened for phobias prior to enrollment.

Incidental Findings: The technologist completing the MRI scan will review each structural scan for any gross abnormalities. If any suspected abnormality is detected, the technologist will have the scan reviewed by a physician in order to determine whether the participant should be informed. If the physician determines that the abnormality should be followed up, the study team will notify the participant that a potential abnormality was detected on their brain scan and encourage them to follow up with their health care provider.

In summary, risks are low and appropriate safeguards are planned and in place to handle risks in a timely and appropriate manner.

8. Possible Benefits:

There is potential for direct benefit to the participants, as the interventions, either alone or in combination may improve their knee OA symptoms. In addition, the findings from the study could lead to substantial societal benefit in the form of new interventions for knee OA pain. Knee OA is the most common form of OA and produces substantial disability and reduced quality of life. Minority groups, especially African Americans, appear to be disproportionately impacted. Given this prevalence and enormous societal impact, this study aims to target factors contributing to ethnic

group difference in pain and disability associated with knee OA. This information has the potential to improve treatment of knee OA in the future and to reduce ethnic/racial disparities in OA pain.

Importance of the Knowledge to Be Gained

The information obtained will provide novel and important information regarding the benefits of two interventions that target the biological and psychosocial factors contributing to ethnic differences in OA-related pain and disability. This will provide the foundation for more informed intervention strategies in the future, which may reduce racial and ethnic disparities in OA pain and disability.

Inclusion of Women and Minorities

Ethnic differences are a major aspect of the proposed research; therefore, both African Americans and non-Hispanic whites will be equally represented, each comprising half of the total sample. Other ethnic groups will not be included in this study, given the focus of the research; however, our goal is to extend the work to other minority groups in the future. Both sexes will be included, and we anticipate enrolling more women (60-65%) than men (35-40%), but recruitment will be monitored to ensure equal sex ratios in each ethnic group.

Data and Safety Monitoring Plan

While this is not an efficacy trial, this does meet the definition of a clinical trial. The trial will be registered in ClinicalTrials.gov. Therefore, we will establish a Data Safety and Monitoring Board (DSMB) comprised of experts who are external to the project to monitor the project. The DSMB will perform the following functions:

- Review the research protocol, informed consent documents and plans for data safety and monitoring;
- Evaluate the progress of the trial, including periodic assessments of data quality and timeliness, recruitment, accrual and retention, participant risk versus benefit, performance of the trial sites, and other factors that can affect study outcome;
- Consider factors external to the study when relevant information becomes available, such as scientific or therapeutic developments that may have an impact on the safety of the participants or the ethics of the trial;
- Review study performance, make recommendations and assist in the resolution of problems reported by the Principal Investigator;
- Protect the safety of the study participants;
- Report to NIA on the safety and progress of the trial;
- Make recommendations to the NIA and the Principal Investigator concerning continuation, termination or other modifications of the trial based on the observed beneficial or adverse effects of the treatment under study;
- Ensure the confidentiality of the study data and the results of monitoring; and,
- Assist the NIA by commenting on any problems with study conduct, enrollment, sample size, and/or data collection.

Progress reports summarizing study enrollment, adverse events, data quality, and intervention fidelity will be provided to the NIA and DSMB at least annually. The DSMB will review these reports and hold a teleconference with the study investigators to review the outcomes. The DSMB will provide the NIA and study team a written report with recommendations after each teleconference. Any subsequent recommendations regarding protocol changes will be addressed by the study team. In addition to reporting to the DSMB and NIA, all adverse events will be reported to the IRBs at each institution for their review. Also, the investigators will monitor reported adverse events on an ongoing basis and consider protocol modifications to minimize risks to the study subjects.

9. Conflict of Interest

None

Literature Cited:

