Mindfulness-induced analgesia was associated with decreased activation in brain regions subserving pain perception and increased activation in brain regions involved in cognitive pain modulation (5, 24). In addition, in collaboration with [name] (University of Texas Health Science Center), we recently conducted a pilot clinical trial testing a 5-day course of active versus sham tDCS in patients with knee OA. Compared to the sham condition, active tDCS produced significant reductions in clinical pain severity with large effect sizes (4). 4) Combined tDCS and BAT May Produce Additive or Synergistic Effects: tDCS is well-recognized as a non-invasive approach to induce neuroplasticity, increasing the brain's ability to adaptively reorganize in response to psychological or behavioral interventions (38, 39). Because the therapeutic effects of mindfulness are at least in part due to adaptive changes in pain-related brain function (i.e. neuroplasticity)(40, 41), applying tDCS concurrent with BAT may augment the adaptive brain changes that occur with BAT. This approach of combining tDCS with cognitive and behavioral interventions is being tested in other clinical populations, including patients with cognitive or motor impairment (42-44). Indeed, a recent study in healthy young adults showed that tDCS combined with brief cognitive therapy produced larger increases in heat pain tolerance than either treatment alone, showing promise for combining tDCS and a cognitively-based pain intervention (45).

5. Hypotheses and Specific Aims:

Based on our scientific premise, we propose to address the following Specific Aims (SA) and hypotheses.

SA1: To determine the independent and combined effects of brief BAT and tDCS interventions (vs. their respective sham conditions) on pain modulatory balance, pain-related brain function, and OA-related pain and disability among AA and NHW adults with symptomatic knee OA.

Hypothesis 1: Compared to the combination of sham BAT and sham tDCS, both tDCS and BAT will:
1a) Enhance pain modulatory balance by reducing pain facilitation and increasing pain inhibition;
1b) Normalize resting and pain-evoked cerebral blood flow in pain-related regions of interest (ROIs);
and 1c) Reduce clinical pain and disability and improve functional performance. We anticipate that the combined treatments will produce the largest effects, showing evidence of additivity or even synergy.

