D3. Data Analysis: Sample Size and Statistical Power: In this study, we are proposing to randomize 360 individuals to four groups defined by a 2X2 factorial design, and we expect to have 320 completers. Table 4 illustrates the effect sizes (Cohen's D) produced by the proposed interventions compared to their sham conditions for different outcomes that have been reported in our previous studies (4, 5). We plan to conduct six primary hypothesis tests (Sham vs Real BAT and Sham vs. Real tDCS for three primary outcomes) with the use of F-test at a corrected $\alpha=0.0083$ significance level. Even with this conservative approach, we have sufficient power for detecting single intervention effects, with power greater than 90% for most outcomes. We do not have effect size estimates for the

combined effect, but our sample size provides 80% power to detect effects as small as Cohen's $D=0.39$.

Table 4: Effect Sizes Observed for tDCS and MMT in our Previous Work				
		Power for Different Sample Sizes		
Outcome	Cohen's D	N = 300	N = 320	N = 340
tDCS (from Ahn, et al)				
CPM	0.34	0.61	0.65	0.68
Pain Rating	0.44	0.88	0.90	0.92
MMT (from Zeidan, et al)				
Heat Pain	0.51	0.97	0.98	0.99
rCBF	0.82	0.99	0.99	0.99

Statistical Analysis Plan:

Summary statistics will be calculated by group for demographic characteristics and all predictor and outcomes measures at baseline and follow-up. Statistical inference will be conducted for the three primary aims as follows.

For **Aim 1**, we will test the effects of BAT, tDCS, and their interaction upon outcomes. For hypotheses 1a-1c, our primary outcomes will be pain modulatory balance (ratio of CPM to temporal summation), pain-evoked cerebral activation, and clinical pain, respectively. Intention-to-treat analysis will be conducted using appropriate linear contrasts to test for intervention effects accounting for interaction terms based on general linear models with covariate adjustment for site, sex, age, and baseline value. Specifically, for each outcome (Y), the model will be:

$$E(Y) = \beta_0 + \beta_1 \text{BaselineScore} + \beta_2 \text{Covariates} + \beta_3 \text{BAT} + \beta_4 \text{tDCS} + \beta_5 \text{AA} +$$

$$\beta_6 \text{BAT} * \text{tDCS} + \beta_7 \text{BAT} * \text{AA} + \beta_8 \text{tDCS} * \text{AA} + \beta_9 \text{BAT} * \text{tDCS} * \text{AA},$$

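### Hypothesis 1 compares each treatment with double sham, but the primary tests average over the other treatment, and no rule says which result supports a claim for a treatment alone

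*Combined protocol and SAP*

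**What the plan says.** Section 5 gives two comparators for the same aim. Specific Aim 1 reads "To determine the independent and combined effects of brief BAT and tDCS interventions (vs. their respective sham conditions"), that is, each treatment against its own sham. Hypothesis 1, directly below it, reads "Compared to the combination of sham BAT and sham tDCS, both tDCS and BAT will" improve the three outcome domains, which makes the double-sham cell the reference. It continues: "We anticipate that the combined treatments will produce the largest effects, showing evidence of additivity or even synergy".

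Section D3 (sample size) defines six primary tests: "Sham vs Real BAT and Sham vs. Real tDCS for three primary outcomes". The Aim 1 analysis says "Linear contrast will be employed to test the main effect of BAT" and gives the contrast as beta3 + beta6/2 + beta7/2 + beta9/4; the tDCS contrast is beta4 + beta6/2 + beta8/2 + beta9/4. On coding it states "where BAT and tDCS are dummy variables for interventions, AA is the dummy variable for African Americans".

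The same section lists the BAT-by-tDCS interaction among the effects to be tested. It also promises point estimates and 95% intervals for each treatment with and without the other, overall and by race. It gives the interaction no significance level, sets no test of a treatment alone against double sham, and does not say how to read a significant main effect when an interaction is present.

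**The concern.** A significant main effect of BAT answers whether real BAT beats sham BAT on average, when half of participants also receive real tDCS. Hypothesis 1 as worded asks whether BAT alone beats receiving neither treatment. Someone reporting the trial against its stated hypothesis could cite the first result as proof of the second. Under synergy it need not be: part of the main effect, or all of it, may come from the combination cell. Aim 1 asks for independent as well as combined effects, so what each treatment does alone is part of the question.

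The power statement has the same gap. It covers single-intervention effects, but its figures belong to the averaged comparison, which uses twice as many participants per side as the comparison with double sham.

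**Working it through.** **Inputs.** 360 randomised equally to four cells (Table 1); 320 completers expected, so about 80 per cell and 160 per margin if attrition is even; alpha 0.0083; D = 0.34, 0.44 and 0.51 (Table 4). D is in SD units, without allowance for baseline adjustment.

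**1. What each contrast estimates.** With 0/1 coding and the races weighted equally:
- BAT effect under sham tDCS (BAT alone against double sham): beta3 + beta7/2.
- BAT effect under real tDCS: beta3 + beta7/2 + beta6 + beta9/2.
- Mean of the two: beta3 + beta6/2 + beta7/2 + beta9/4, which is the primary contrast.

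The primary contrast minus the double-sham contrast is beta6/2 + beta9/4, half the race-averaged BAT-by-tDCS interaction. For tDCS the difference is the same, with beta4 + beta8/2 as the double-sham contrast. It is zero under additivity.

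**2. Reproducing the plan's power.** For 160 against 160, the standard error of the difference is 2/√320 = 0.112 SD. A two-sided noncentral t calculation at 0.0083 gives 0.65, 0.90 and 0.97 for D = 0.34, 0.44 and 0.51; Table 4 shows 0.65, 0.90 and 0.98 at N = 320. The 80%-power effect is (2.64 + 0.84) × 0.112 = 0.39, as stated. So Table 4 and the 0.39 are main-effect figures. The sample-size text describes tests "with the use of F-test at a corrected" level, while the analysis text says they "will be performed at one-sided" 0.0083. One-sided 0.0083 does not reproduce the D = 0.34 and 0.44 rows (0.74 and 0.94 by normal approximation), so two-sided is used below, with one-sided figures noted.

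**3. Power for Hypothesis 1 as worded.** For 80 against 80, the standard error is √(2/80) = 0.158 SD.

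| D | 160 vs 160 | 80 vs 80 |
|---|---|---|
| 0.34 | 0.65 | 0.30 |
| 0.44 | 0.90 | 0.54 |
| 0.51 | 0.97 | 0.71 |

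The 80%-power effect for 80 against 80 is (2.64 + 0.84) × 0.158 = 0.55 by normal approximation, or 0.56 by noncentral t. One-sided, by normal approximation, power is 0.40, 0.65 and 0.80, and the 80%-power effect is 0.51.

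**4. A combination-only pattern (assumed effects).** The documents give no combined effect size. Suppose a treatment has no effect alone and adds D on top of the other. Its main effect is then D/2, while its effect against double sham is 0.

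| Assumed D | Main effect | Main effect significant, two-sided | One-sided |
|---|---|---|---|
| 0.5 | 0.25 | 34% | 43% |
| 0.6 | 0.30 | 51% | 61% |
| 0.8 | 0.40 | 82% | 88% |

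A simulation of the plan's contrast (40 per cell and race, 20,000 runs, with neither treatment active alone) agrees where run: 33% for BAT at D = 0.5 and 80% at D = 0.78. In the same runs the double-sham contrast rejected in 0.8% to 0.9%, close to its nominal 0.83%.

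**The case against.** The main-effect tests are the standard analysis of a 2×2 factorial. They are written out in full and match Aim 1 and the definition of the six tests. Only the lead-in to Hypothesis 1 names double sham. This stands: the wording of the hypothesis is out of step, not the test.

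A reader might infer that the plan counts on synergy. It does not: it anticipates additivity or possibly synergy, and under additivity the two comparisons are identical.

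A reader might also infer that a combination-only effect would go unseen. The documents do not support that. The planned effect of each treatment without the other, in the whole sample, is exactly beta3 + beta7/2 or beta4 + beta8/2. At an assumed D of 0.8, the interval for the treatment alone would centre on 0 with half-width about 1.96 × 0.158 = 0.31 SD, and the interval with the other treatment would centre on 0.8. The interaction has standard error 4/√320 = 0.224 SD, so its test has power 0.82 at two-sided 0.0083, or 0.95 at 0.05; both levels are assumptions, since the plan sets none.

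Finally, 0.8 SD is a favourable choice. It exceeds every non-imaging effect in Table 4, and no effect alone runs against the single-treatment effects listed there. Hence the range shown.

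Still unanswered: neither the intervals nor the interaction is among the six tests, and nothing says that a claim against double sham must rest on them.

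**Conclusion.** The point holds as a mismatch between the hypothesis and the effect tested, with no rule for interpretation. It is not a fault in the primary analysis. A reader might call the 82% a false-positive rate. It is not one: in that scenario the averaged effect really is 0.40, and rejecting is correct for the contrast tested. The error would lie in reporting the result as support for Hypothesis 1 as worded. Nor is the low 80-against-80 power a shortfall of the primary tests, since no such test is planned; it shows that the stated power cannot be carried over to Hypothesis 1 as written.

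The size depends on the interaction: nothing under additivity, and 34% to 82% for combination-only effects of 0.5 to 0.8 SD. The loss of power for the double-sham comparison, for example from 0.90 to 0.54 at D = 0.44, does not depend on the assumed synergy. All figures assume 80 completers per cell. Imaging is planned in about two-thirds of the sample, so cells for the cerebral activation outcome will be smaller.

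**What to change.** 1. Reword Hypothesis 1 so that each treatment is compared with its own sham, averaged over the other treatment and race, as in Aim 1 and the primary contrasts.
2. Add to the Aim 1 analysis that any claim for a treatment alone against double sham rests on the already planned simple-effect estimate and its 95% interval (beta3 + beta7/2 for BAT, beta4 + beta8/2 for tDCS), reported beside the main effect and the interaction.
3. State in the sample-size text that Table 4 and the 0.39 apply to main effects only, and that a comparison of two single cells, including the combination against double sham, has 80% power at about D = 0.56.

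All the contrasts come from the model already specified, so no participants, visits or data are added and the six primary tests are unchanged. The cost is that single-treatment claims become more modest. Keeping Hypothesis 1 as worded and powering it would be far dearer: 80% power at D = 0.44 needs 126 completers per cell, or 4 × 126 = 504, against 320 planned.
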